6.2. Exclusion Criteria

Subjects will be excluded from study enrollment if they meet any of the following criteria within the screening period, which is ≤ 28 days prior to the start of study treatment, unless specifically defined:

Study Disease Conditions or Treatments

- [14] have complications of Crohn's disease such as strictures, stenoses, or any other manifestation for which surgery might be indicated or could confound the evaluation of efficacy
- [15] diagnosis of conditions affecting the digestive tract, such as UC, indeterminate colitis, fistulizing disease, abdominal or perianal abscess, adenomatous colonic polyps not excised, colonic mucosal dysplasia, and short bowel syndrome

- [16] have had any kind of bowel resection, diversion, or placement of a stoma within 6 months or any other intra-abdominal surgery within 3 months prior to screening
- [17] have received any of the following for treatment of Crohn's disease:
- 6-thioguanine (6-TG), cyclosporine, tacrolimus, sirolimus, pentoxifylline, or mycophenolate mofetil within 8 weeks prior to baseline
 - corticosteroid enemas, IV corticosteroids, corticosteroid suppositories, or topical treatment within 3 weeks prior to screening colonoscopy
 - rectal 5-ASA within 3 weeks prior to screening colonoscopy
 - have used apheresis (for example, Adacolumn apheresis) ≤ 2 weeks prior to screening.
- [18] have previous exposure to any biologic therapy targeting IL-23 p19 either licensed or investigational, or prior exposure to ustekinumab
- [19] have received natalizumab or agents that deplete B or T cells (for example, rituximab, alemtuzumab, or visilizumab) within 12 months of screening, or, if after receiving these agents, evidence is available at screening of persistent depletion of the targeted lymphocyte population
- [20] have been treated with any investigational drug for Crohn's disease within 8 weeks prior to baseline or 5 half-lives of the drug (whichever is longer), OR with interferon therapy within 8 weeks before baseline

General Eligibility Criteria

- [21] have evidence of active or latent tuberculosis (TB) (refer Section 9.5.4.1 for details on full TB exclusion criteria)
- [22] have had any malignancy within 5 years of screening, except for basal cell or squamous epithelial carcinoma of the skin that has been resected with no evidence of metastatic disease for at least 3 years OR cervical carcinoma in situ with no evidence of recurrence within 5 years of screening
- [23] have an abnormality in the 12-lead ECG that, in the opinion of the investigator, increases the risks associated with participating in the study
- [24] increases the risks associated with participating in the study if the presence or history within 12 months prior to screening of significant uncontrolled cerebrocardiovascular (for example, myocardial infarction, unstable angina, unstable arterial hypertension, moderate-to-severe heart failure [New York Heart Association class III/IV], or cerebrovascular accident); presence of respiratory, hepatic, renal, gastrointestinal, endocrine, hematologic, or abnormal laboratory values at screening that, in the opinion of the investigator, pose an unacceptable risk to the subject if participating in the study or of interfering with the interpretation of data

- [25] presence of significant uncontrolled neuropsychiatric disorder, have history of a suicide attempt or have a score of 3 on Item 12 (Thoughts of Death or Suicide) of the Quick Inventory of Depressive Symptomatology–Self Report (16 Items) (QIDS-SR16) at screening (Visit 1) or baseline (Week 0; Visit 2)
- [26] are investigator site personnel directly affiliated with this study and/or their immediate families. Immediate family is defined as a spouse, parent, child, or sibling, whether biological or legally adopted.
- [27] are Lilly employees or employees of third-party organizations (TPOs) involved with the study
- [28] are currently enrolled in a clinical trial involving an investigational product or nonapproved use of a drug or device, OR are concurrently enrolled in any other type of medical research not scientifically or medically compatible with this study, per investigator judgment
- [29] have previously completed or withdrawn from this study or any other study investigating LY3074828. This criterion does not apply to subjects undergoing rescreening procedures.
- [30] have received live, attenuated vaccine(s) within 2 months of screening or intend to receive such during the study; vaccines should be avoided for 2 months after the last dose of study drug. Uses of nonlive (inactivated) vaccinations are allowed for all subjects.
- [31] have human immunodeficiency virus/acquired immune deficiency syndrome (HIV/AIDS) or test positive for antibodies at screening
- [32] have hepatitis B or test positive for hepatitis B virus (HBV) at screening, defined as: (1) positive for hepatitis B surface antigen or (2) positive for anti-hepatitis B core antibody (HBcAb+) and positive confirmatory polymerase chain reaction (PCR) for HBV, regardless of anti-hepatitis B surface antibody status
- [33] have hepatitis C or test positive hepatitis C virus at screening, defined as: positive result for hepatitis C antibody and positive confirmatory PCR test for hepatitis C virus
- [34] had Clostridium difficile (C diff) infection within 60 days of screening or test positive at screening, or other intestinal pathogen with 30 days before screening endoscopy. Subject must not have signs of an ongoing infection related to an intestinal pathogen.
- [35] have any clinically significant extra-intestinal infection or opportunistic, chronic, or recurring infection within 6 months before screening. Examples include but are not limited to infections requiring IV antibiotics, hospitalization, or prolonged treatment.
- [36] have received a systemic (including oral) anti-infective agent for an infection within 28 days of baseline

- [37] are pregnant, lactating, or planning pregnancy (both men and women) while enrolled in the study, or within 3 months after receiving the last dose of study agent
- [38] have significant allergies to humanized monoclonal antibodies or any components of the LY3074828 product formulation
- [39] history of alcohol or other drug abuse within the last year
- [40] are unsuitable for inclusion in the study in the opinion of the investigator or sponsor for any reason that may compromise the subject's safety or confound data interpretation.

6.3. Lifestyle Restrictions

Study participants should be instructed not to donate blood or blood products during the study or for 16 weeks following their last dose.

6.4. Screen Failures

Individuals who do not meet the criteria for participation in this study (screen failure) may be rescreened. Subjects may be rescreened due to the following criteria [1], [2], [3], [4], [5], [6], [7], [8], [9], [10], [11], [12], [13], [14], [16], [17], [19], [20], [21], [22], [23], [24], [26], [27], [28], [29], [30], [34], [35], [36], [37], or [39]. Individuals may be rescreened up to 2 times. Each time rescreening is performed, the individual must sign a new informed consent form (ICF) and will be assigned a new identification number.

7. Treatments

7.1. Treatments Administered

Table AMAG.3 shows the treatment regimens.

Table AMAG.3. Treatment Regimens

Treatment Group	Description
Period 1 (Double Blind)	
LY Dose Arm 1	1000 mg IV LY Q4W
LY Dose Arm 2	600 mg IV LY Q4W
LY Dose Arm 3	200 mg IV LY Q4W
Placebo	Placebo given IV Q4W
Period 2 (Double Blind and Double Dummy)	
LY Dose Arm 1	1000 mg IV LY Q4W* or 300 mg SC LY Q4W*
LY Dose Arm 2	600 mg IV LY Q4W* or 300 mg SC LY Q4W*
LY Dose Arm 3	200 mg IV LY Q4W* or 300 mg SC LY Q4W*
LY Subjects with no Week 12 SES-CD improvement	1000 mg IV Q4W + SC Placebo Q4W
Placebo	1000 mg IV Q4W+ SC Placebo Q4W
Period 3 (Open Label)	
LY Dose Arm 1	300 mg SC LY Q4W
LY Dose Arm 2	300 mg SC LY Q4W
LY Dose Arm 3	300 mg SC LY Q4W
Placebo	300 mg SC LY Q4W

Abbreviations: IV = intravenous; LY = LY3074828; Q4W = every 4 weeks; SC = subcutaneous.

* Also administer the placebo by the appropriate route; for example, if active LY is administered intravenously, then administer placebo via SC route, and vice versa. Administer IV preparation first, followed by SC preparation.

Intravenous infusion of mirikizumab or placebo will occur over at least 2 hours. All patients receiving IV infusion should be monitored for 1 hour or longer (per investigator discretion or local standard of care) after IV dosing is complete. Sites must have resuscitation equipment, emergency medications, and appropriately trained staff available during the infusion and monitoring period. Detailed instructions for investigational product administration will be provided separately by the sponsor.

Subcutaneous administration of mirikizumab or placebo will be given in 3 injections. Detailed instructions regarding supplies and preparation and handling of LY3074828 will be provided by the sponsor.

The investigator or his/her designee is responsible for the following:

- explaining the correct use of the investigational agent(s) to the site personnel
- verifying that instructions are followed properly
- maintaining accurate records of investigational product dispensing and collection

- at the end of the study, returning all unused medication to Lilly, or its designee, unless the sponsor and sites have agreed all unused medication is to be destroyed by the site, as allowed by local law.

7.1.1. Packaging and Labeling

LY3074828 will be supplied to the investigator by Lilly. Clinical trial materials are manufactured in accordance with good manufacturing practices. All investigational products will be stored, inventoried, reconciled, and destroyed according to applicable regulations.

LY3074828 is supplied for clinical trial use as lyophilized powder in a glass vial and should be stored in refrigerated conditions (2°C to 8°C). The vial is manufactured to deliver 75 mg of LY3074828 and will be reconstituted with sterile water for injection and further diluted with normal saline (0.9% sodium chloride) before administration. Placebo will be sterile normal saline (0.9% sodium chloride for injection).

When reconstituted and in a syringe, LY3074828 cannot be distinguished visually from placebo.

Detailed instructions regarding supplies and preparation and handling of LY3074828 will be provided by the sponsor.

Clinical trial materials will be labeled according to the country's regulatory requirements.

7.2. Method of Treatment Assignment

Subjects who meet all criteria for enrollment will be randomized to treatment at Visit 2.

Assignment to treatment groups will be determined by a computer-generated random sequence using an interactive web-response system (IWRS). To achieve between-group comparability, subjects will be stratified to these arms based upon their prior therapy (below); this stratification will be controlled by IWRS.

- A minimum of approximately 30% of subjects will be naive to biologic Crohn's disease therapy (including experimental biologic Crohn's disease therapy).
- At least 50% of the subjects will be prior biologic Crohn's disease therapy-experienced (including experience with experimental biologic Crohn's disease therapy).
- For Period 2, subjects assigned to LY3074828 at baseline will be randomized to either baseline treatment assignment or 300 mg SC LY3074828 Q4W —except for all subjects in the placebo group, and subjects in the LY3074828 treatment groups who have not had any improvement in SES-CD score from baseline at Week 12 (determined by the central reader), who will receive 1000 mg IV LY3074828 Q4W. All subjects will receive IV and SC administration of either LY3074828 or placebo during Period 2 in a double-dummy design. The randomization will be stratified based on endoscopic response (as defined for the primary endpoint).

7.2.1. Selection and Timing of Doses

The actual time of all dose administrations will be recorded in the subject's case report form (CRF). All study procedures (including blood tests) are to be performed predose unless otherwise specified in the Schedule of Activities.

7.3. Blinding

This is a double-blind study; to preserve the blinding of the study, a minimum number of Lilly personnel will see the randomization table and treatment assignments before the study is complete. Only a study site pharmacist or other trained person will be unblinded at the site for investigational product preparation.

Emergency unblinding for AEs may be performed through the IWRS, which may supplement or take the place of emergency codes generated by a computer drug-labeling system. This option should be used ONLY if the subject's well-being requires knowledge of the subject's treatment assignment. All notifications resulting in an unblinding event are recorded and reported by the IWRS.

If an investigator, site personnel performing assessments, or subject is unblinded, the subject must be discontinued from the study. In cases where there are ethical reasons to have the subject remain in the study, the investigator must obtain specific approval from a Lilly clinical research physician (CRP) for the subject to continue in the study.

In case of an emergency, the investigator has the sole responsibility for determining if unblinding of a subject's treatment assignment is warranted. Subject safety must always be the first consideration in making such a determination. If the investigator decides that unblinding is warranted, the investigator should make every effort to contact the Lilly CRP prior to unblinding a subject's treatment assignment unless this could delay emergency treatment of the subject. If a subject's treatment assignment is unblinded, Lilly must be notified immediately.

7.4. Dosage Modification

Dose adjustments are not permitted in this study, except as noted in Section 7.8.2.

7.5. Preparation/Handling/Storage/Accountability

Detailed instructions regarding supplies and preparation and handling of LY3074828 will be provided by the sponsor.

7.6. Treatment Compliance

Every attempt will be made to select subjects who have the ability to understand and comply with study instructions. The investigator is responsible for discussing methods to ensure high treatment compliance with the subject before randomization.

All doses of study medication will be administered at the study site. Deviation(s) from the prescribed dosage regimen should be recorded in the CRF.

If a subject is noncompliant with study procedures and/or investigational product administration, the investigator should assess the subject to determine the reason for noncompliance and educate and/or manage the subject as appropriate to improve compliance. If, in consultation with Lilly or its designee, the noncompliance is deemed to be significant or if further noncompliance occurs, the subject should be discontinued from the study. A subject will be considered noncompliant if he or she fails to attend for administration of study medication within the required treatment window as defined in the Schedule of Activities (Section 2).

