Abbreviations: BMC = bowel movement count; BP = blood pressure; C diff = *Clostridium difficile*; CBC = complete blood count; CDAI = Crohn’s Disease Activity Index; **CCI**; CXR = chest X-ray; DNA = deoxyribonucleic acid; ECG = electrocardiogram; ET = Early Termination; FACIT-Fatigue = Functional Assessment of Chronic Illness Therapy–Fatigue; FSH = follicle-stimulating hormone; HBcAb = anti-hepatitis B core antibody; HBsAb = hepatitis B surface antibody; HBsAg = hepatitis B surface antigen; HBV = hepatitis B virus; HCV = hepatitis C virus; HIV = human immunodeficiency virus; hsCRP = high-sensitivity C-reactive protein; HR = heart rate; IBDQ = Inflammatory Bowel Disease Questionnaire; **CCI**; **CCI** NRS = Numeric Rating Scale; PCR = polymerase chain reaction; PK = pharmacokinetic; PGRC = Patient’s Global Rating of Change; PGRS = Patient’s Global Rating of Severity; PPD = purified protein derivative; Q = Question; QIDS-SR16 = Quick Inventory of Depressive Symptomatology–Self Report (16 Items); RNA = ribonucleic acid; SES-CD = Simple Endoscopic Score for Crohn’s Disease; SF-36 = Medical Outcomes Study 36-Item Short Form Health Survey; temp. = temperature; TB = tuberculosis; UV = unscheduled visit; V = visit.

- a Subjects who discontinue early (before V804) should have all of the V804 procedures completed at the last visit attended.
- b At V3 and V5, collect a hematology sample for CBC only, do not collect serum chemistries. Complete blood count is also collected at all unscheduled visits.
- c Use this visit for patients who are seen by the investigator or site staff at a time point not required by the protocol (i.e., an unscheduled visit) due to disease exacerbation or an adverse event. Procedures or laboratory tests may be performed at unscheduled visits at the discretion of the investigator.
- d Stool samples should not be collected on days of bowel prep or endoscopy/colonoscopy. The stool samples may be collected up to 3 days before bowel prep at Visits 7 and 18.

3. Introduction

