If a patient experiences a fever-associated reaction consisting of headache, rigors and/or temperature $>38^{\circ}\text{C}$ (in the absence of signs or symptoms of a systemic hypersensitivity event) during or up to 6 hours after an infusion of study drug, the following guidance should be followed:

- Study drug infusion should be interrupted and appropriate medical care should be administered (for example, nonsteroidal anti-inflammatory drugs [NSAIDs], antipyretics or antihistamines).
- Additional immunogenicity, PK, and hypersensitivity markers samples should be collected as follows:
 - As soon as possible after the event occurs
 - 4 weeks after the event
 - 12 weeks after the event
- Resumption of study drug infusion after interruption, possibly at a slower rate of administration, can be considered if symptoms resolve and it is deemed to be medically appropriate based on the investigator's discretion, and considering the risk/benefit of readministration.
- Patient should remain in observation, as is clinically appropriate for the patient's symptoms.
- Premedication prior to subsequent study drug administration may be considered, if judged by the investigator to be appropriate for the individual patient.
- If the patient discontinues study drug but remain in the study, management should follow as outlined in Section 8.1.1, and immunogenicity, PK, and hypersensitivity markers should be collected at 4 and 12 weeks after the event.

- If the patient discontinues from the study early for any reason, they should return to complete 4 and 12 week follow-up immunogenicity, PK, and hypersensitivity markers collections.
- If the patient develops systemic hypersensitivity symptoms or signs, they should be managed as described above for a systemic hypersensitivity event.

Infusion Site Reactions

If a patient experiences an infusion site reaction, including urticaria, pruritus, or angioedema localized to the IV infusion site (in the absence of systemic hypersensitivity signs or symptoms), during or up to 6 hours after an infusion of study drug, the following guidance should be followed:

- Study drug infusion should be interrupted and appropriate medical care should be administered (for example, NSAIDS, anti-pyretics or antihistamines).
- Additional immunogenicity, PK, and hypersensitivity markers samples should be collected as follows:
 - As soon as possible after the event occurs
 - 4 weeks after the event
 - 12 weeks after the event

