8.1. Discontinuation from Study Treatment

8.1.1. *Permanent Discontinuation from Study Treatment*

Discontinuation of the investigational product for abnormal liver tests should be considered by the investigator when a subject meets one of the following conditions after consultation with the Lilly designated medical monitor:

- ALT or AST >8xULN
- ALT or AST >5xULN for more than 2 weeks
- ALT or AST >3xULN and TBL >2xULN or prothrombin time >1.5xULN
- ALT or AST >3xULN with the appearance of fatigue, nausea, vomiting, right upper-quadrant pain or tenderness, fever, rash, and/or eosinophilia (>5%)
- ALP >3xULN
- ALP >2.5xULN and TBL >2xULN
- ALP >2.5xULN with the appearance of fatigue, nausea, vomiting, right quadrant pain or tenderness, fever, rash, and/or eosinophilia (>5%).

Subjects may discontinue treatment for any of the reasons noted above, or for other reasons such as the development of a serious adverse event. To better communicate patient flow throughout the study, different study period situations are provided below:

- Subjects who discontinue the investigational product in Period 1 or Period 2 may continue in the study according to the visit schedule (Section 2).
- At Week 52/Visit 18, subjects who have previously discontinued the investigational product will continue to Visit 801 of the Follow-up Period.
- Subjects who discontinue the investigational product in Period 3 may continue in Period 3 and then proceed to Week 104/Visit 801 of the Follow-up Period.

Investigational product is to be discontinued for patients who experience clinically significant systemic hypersensitivity events (such as anaphylaxis) following administration of investigational product.

8.1.2. *Discontinuation of Inadvertently Enrolled Subjects*

If the sponsor or investigator identify a subject who did not meet enrollment criteria and was inadvertently enrolled, a discussion must occur between the sponsor CRP and the investigator to determine if the subject may continue in the study. If both agree it is medically appropriate to continue, the investigator must obtain documented approval from the sponsor CRP to allow the inadvertently enrolled subject to continue in the study with or without treatment with investigational product.

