9.3.1. Serious Adverse Events

An SAE is any AE from this study that results in one of the following outcomes:

- death
- initial or prolonged inpatient hospitalization
- a life-threatening experience (that is, immediate risk of dying)
- persistent or significant disability/incapacity
- congenital anomaly/birth defect
- important medical events that may not be immediately life-threatening or result in death or hospitalization but may jeopardize the patient or may require intervention to prevent one of the other outcomes listed in the definition above. Examples of such medical events include allergic bronchospasm requiring intensive treatment in an emergency room or at home, blood dyscrasias or convulsions that do not result in inpatient hospitalization, or the development of drug dependency or drug abuse.

Although all AEs occurring after signing the ICF are recorded in the eCRF, SAE reporting begins after the subject has signed the ICF and has received investigational product. However, if an SAE occurs after signing the ICF, but prior to receiving investigational product, it needs to be reported ONLY if it is considered reasonably possibly related to study procedure.

Study site personnel must alert Lilly or its designee of any SAE within 24 hours of investigator awareness of the event via a sponsor-approved method. If alerts are issued via telephone, they are to be immediately followed with official notification on study-specific SAE forms. This 24-hour notification requirement refers to the initial SAE information and all follow-up SAE information.

Pregnancy (during maternal or paternal exposure to investigational product) does not meet the definition of an AE. However, to fulfill regulatory requirements any pregnancy should be reported following the SAE process to collect data on the outcome for both mother and fetus.

Investigators are not obligated to actively seek AEs or SAEs in subjects once they have discontinued and/or completed the study (the subject summary CRF has been completed). However, if the investigator learns of any SAE, including a death, at any time after a subject has been discharged from the study, and he/she considers the event reasonably possibly related to the study treatment or study participation, the investigator must promptly notify Lilly.

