IBDQ	Inflammatory Bowel Disease Questionnaire
ICF	informed consent form
ICH	International Council for Harmonisation
IgG	immunoglobulin G
IL	interleukin
interim analysis	An interim analysis is an analysis of clinical study data, separated into treatment groups, that is conducted before the final reporting database is created/locked.
investigational product	A pharmaceutical form of an active ingredient or placebo being tested or used as a reference in a clinical trial, including products already on the market when used or assembled (formulated or packaged) in a way different from the authorized form, or marketed products used for an unauthorized indication, or marketed products used to gain further information about the authorized form.
ITT	intention to treat: The principle that asserts that the effect of a treatment policy can be best assessed by evaluating on the basis of the intention to treat a subject (that is, the planned treatment regimen) rather than the actual treatment given. It has the consequence that subjects allocated to a treatment group should be followed up, assessed, and analyzed as members of that group irrespective of their compliance to the planned course of treatment.

IV	intravenous
IVRS/IWRS	interactive voice-response system/interactive web-response system
MedDRA	Medical Dictionary for Regulatory Activities
MTX	methotrexate
NOAEL	no-observed-adverse-effect level
NSAIDS	nonsteroidal anti-inflammatory drugs
NRI	non-responder imputation
CCI	
PCR	polymerase chain reaction
PD	pharmacodynamics
PGRC	Patient's Global Rating of Change (Crohn's disease)
PGRS	Patient's Global Rating of Severity (Crohn's disease)
PK	pharmacokinetics
PPD	purified protein derivative
PRO/ePRO	patient-reported outcomes/electronic patient-reported outcomes
PRO2	Patient Reported Outcome2: a 2-item index comprised of the SF and AP items from the CDAI
PT	preferred term
Q4W	every 4 weeks
QIDS-SR16	Quick Inventory of Depressive Symptomatology–Self Report (16 Items)
SAE	serious adverse event
SAP	statistical analysis plan
SC	subcutaneous
screen	The act of determining if an individual meets minimum requirements to become part of a pool of potential candidates for participation in a clinical study.
SES-CD	Simple Endoscopic Score for Crohn's Disease
SF	stool frequency
SF-36	Medical Outcomes Study 36-Item Short Form Health Survey

SOC	system organ class
SUSARs	suspected unexpected serious adverse reactions
TB	tuberculosis
TBL	total bilirubin level

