NOTE:

Period 1:

- Subjects who discontinue treatment may continue in the study according to the visit schedule into Period 2.
- In IWRS these subject will be randomized as “No treatment for Period 2.”.
- Subjects who ETV will continue to Visit 804/ET.

Period 2:

- Subjects who discontinue treatment may continue in the study according to the visit schedule during Period 2.
- At Week 52/Visit 18, subjects who have previously discontinued treatment or do not have clinical benefit will continue to Visit 801 of the Follow-up Period.
- Subjects who ETV will continue to Visit 804/ET.

Period 3:

- Subjects who discontinue treatment in Period 3 may continue in Period 3 and then proceed to Week 104/Visit 801 of the Follow-up Period.

Figure AMAG.5.1. Study design.

6. A Priori Statistical Methods

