6.1. General Considerations

Statistical analysis of this study will be the responsibility of Eli Lilly and Company (Lilly) or its designee.

Continuous data will be summarized in terms of the number of observations, mean, standard deviation (SD), minimum, median, and maximum. Categorical data will be summarized in terms of the number of subjects in the analysis population, the number of subjects providing data at the relevant time point, frequency counts, and the percentages corresponding to the appropriate method. All confidence intervals (CIs) and statistical tests will be 2-sided unless otherwise specified.

All tests of the primary and secondary treatment effects, including health outcomes measurements will be conducted at a 2-sided alpha level of 0.10, unless otherwise stated.

The Schedule of Activities outlined in the protocol specifies the allowable windows for assessments. Assessments performed outside these windows are not expected to affect the primary outcomes and, as such, no subject /assessment will be excluded from any analysis due to this reason.

Data collected at early termination (ETV) visits will be entered under the visit in which it occurs. For by-visit summaries, only visits in which a measure was scheduled to be collected will be summarized.

Data summaries, analyses of results, and listings will be generated using SAS[®] Version 9.2 or later. Pharmacokinetic/pharmacodynamic (PK/PD) analyses will be carried out using other appropriate software. Not all displays described in this SAP will necessarily be included in the clinical study reports (CSRs). Not all displays will necessarily be created as a “static” display. Some may be incorporated into interactive display tools instead of or in addition to a static display. Any display described in this statistical analysis plan (SAP) and not provided will be available upon request.

Any change to the data analysis methods described in the protocol will require an amendment ONLY if it changes a principal feature of the protocol. Any other change to the data analysis methods described in the protocol, and the justification for making the change, will be described in the CSR. Additional exploratory analyses of the data will be conducted as deemed appropriate.

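### Protocol 7.6 makes leaving the study the default for significant or repeated noncompliance, although the plan already lets subjects stop drug and keep their visits

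*Protocol*

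**What the plan says.** Protocol 7.6 asks the investigator to find the reason for noncompliance and to educate or manage the subject. If the noncompliance is then deemed significant in consultation with the sponsor, or "if further noncompliance occurs, the subject should be discontinued from the study". The clause covers study procedures as well as dosing, and failing to attend within a dosing window is enough. It does not mention stopping drug only.

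Protocol 8.1.1 gives another route. A subject who stops drug in Period 1 or 2 may stay on the visit schedule and moves to Visit 801 at Week 52. One who stops in Period 3 may stay in that period and then enter follow-up. The route is open for the listed liver criteria and for other reasons. The design notes in SAP Section 5 repeat it for Period 1 ("Subjects who discontinue treatment may continue in the study according to the visit schedule into Period 2") and provide an IWRS status of no treatment in Period 2.

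Under footnote a of the Schedule of Activities, a subject who leaves early "should have all of the V804 procedures completed at the last visit attended". Protocol 9.3.1 adds: "Investigators are not obligated to actively seek AEs or SAEs in subjects once they have discontinued and/or completed the study". After a fever-associated or infusion-site reaction, 7.8.2.2 still asks early leavers back: "they should return to complete 4 and 12 week follow-up immunogenicity, PK, and hypersensitivity markers collections". A similar rule holds after a systemic hypersensitivity event. The ITT entry in Appendix 1 states the principle that subjects "should be followed up, assessed, and analyzed as members of that group irrespective of their compliance to the planned course of treatment".

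**The concern.** The wording turns a dosing-attendance problem into a data-collection problem. The Week 4 window is Day 29 ± 3 and the Week 8 window is Day 57 ± 3. A subject dosed 4 days late at both visits meets the recurrence branch, which has no severity threshold. That subject does attend and could be assessed.

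Removal cuts against the follow-up and assessment part of the Appendix 1 principle, and nothing in the analysis plan asks for it. SAP 6.8 lists noncompliance and counts it as a protocol deviation. SAP 6.17 excludes nobody from ITT for a deviation and plans no per-protocol population. At stake are later continuous outcomes, PK and ADA samples, and safety observation after drug, all of which an existing route could still collect.

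**Working it through.** **1. Primary endpoint.** Protocol 10.1 gives 60 per arm, 35% versus 15%, two-sided alpha 0.10 and 81% power. With pooled variance under the null, power = Φ{[0.20 − 1.645·√(2·0.25·0.75/60)] / √[(0.15·0.85 + 0.35·0.65)/60]} = Φ[(0.20 − 1.645·0.0791)/0.0769] = 81.8%, which reproduces the stated figure. SAP 6.3.1 scores anyone who stops drug before Week 12 as a non-responder, on study or not. If 5% of each arm (assumed) were scored this way, power would be 79.4% under either route. Replacing study removal by drug discontinuation therefore changes nothing here. The same holds for the other endpoints that use this imputation.

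**2. Collections still ahead.** These are counts from the Schedule of Activities for a subject who stays on study off drug to Visit 18 and then attends Visits 801-804. A removed subject has one early-termination set instead.

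| Leaves after | AE | PK | ADA | IBDQ | Weeks to Week 68 |
|---|---|---|---|---|---|
| Week 8 (V6) | 1+11+4 = 16 | 1+8+4 = 13 | 1+5+4 = 10 | 1+5+1 = 7 | 60 |
| Week 24 (V11) | 7+4 = 11 | 4+4 = 8 | 2+4 = 6 | 3+1 = 4 | 44 |
| Week 44 (V16) | 2+4 = 6 | 1+4 = 5 | 1+4 = 5 | 1+1 = 2 | 24 |

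In the Week 8 row the terms are V7, V8-V18 and the follow-up visits. In the other rows they are the rest of Period 2 and follow-up. Week 68 is 52 + 16, assuming Visits 801-804 keep their 4-week spacing after Week 52. All entries are upper bounds. PK and ADA counts matter only for subjects treated with LY3074828.

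**3. Where these data would be used.**
- *Week 12 continuous outcomes.* IBDQ, SF-36 and FACIT-Fatigue are not scheduled at Week 8. SAP 6.1 enters early-termination data under the visit where they occur, and "For by-visit summaries, only visits in which a measure was scheduled to be collected will be summarized". An early-termination questionnaire at Week 8 would not be summarized, and Week 12 would be missing for the ITT MMRM. A Week 12 value from a subject off drug but on study falls inside the window in Table AMAG.6.3, and SAP 6.1.6.3 states no exclusion of such values. The mBOCF sensitivity analysis uses no later data.
- *ADA and PK.* SAP 6.14.6.2 uses all ADA observations after first dose (after first LY3074828 for placebo starters). PK analyses are in a separate plan.
- *Adverse events.* In Table AMAG.6.4 the Period 1, Period 2, All SC LY and All LY (a) windows close no later than the treatment disposition visit. Only All LY (b) runs on after drug, and Table AMAG.6.5 shows it as one pooled group with no comparison.
- *Week 52 health outcomes.* Subjects who stop drug in Period 1 are outside EHO Group 2. Those who stop in Period 2 stay in it, so their observed scores would count, descriptively only. The responder versions use non-responder imputation and do not change.

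**4. How many subjects.** No removal rate is given. Assume that each dosing window is missed independently with chance q, that two misses trigger removal, and that nobody else leaves. Before Week 12 there are 2 windows (Weeks 4 and 8), with probability q². Through Week 48 there are 12, with probability 1 − (1−q)¹² − 12q(1−q)¹¹.

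| q | Before Week 12 | of 180 | By Week 48 | of 180 |
|---|---|---|---|---|
| 1% | 0.0001 | 0.02 | 0.0062 | 1.1 |
| 2% | 0.0004 | 0.07 | 0.0231 | 4.2 |
| 5% | 0.0025 | 0.45 | 0.1184 | 21.3 |

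The significance branch would add to these by an amount the documents do not allow one to estimate.

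**The case against.** The strongest reply is that little of the potential gain would be realized. Protocol 8.2 requires study discontinuation before another effective Crohn's therapy is introduced, and 7.7 restricts concomitant Crohn's treatment to Table AMAG.4. Subjects with active disease who come off drug may soon need such therapy, whatever 7.6 says. This stands, and it is why the visit and week counts are only upper bounds. It also stands that most of the recovered data would be descriptive, that the effect on the Week 12 MMRM is very small, and that a subject who ignores study procedures may give little if retained. The SAP 6.1 statement that out-of-window assessments are not excluded concerns assessments and does not show that late dosing is harmless.

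Discretion also exists. The rule is a *should*, after assessment and education, and 8.1.1 does not shut out noncompliant subjects. That makes 7.6 a default and not an absolute rule, but it still points sites to removal without naming the alternative. Nor is all safety follow-up lost on leaving: Protocol 9.3 keeps the investigator responsible for following serious or related events.

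A reader might infer that 7.6 contradicts the ITT analysis. It does not. Protocol 10.2 keeps every randomized subject in the set, and only the follow-up part of the Appendix 1 principle is affected. A reader might also infer that the rule biases the primary result or lowers its power relative to the alternative. Step 1 shows that, for subjects taken off drug, both routes give the same score.

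**Conclusion.** The point holds as a minor improvement. The default in 7.6 gives up data that an existing on-study route could collect, and no planned analysis benefits. No stated figure is wrong. The avoidable loss is confined to Week 12 continuous values for a few subjects, ADA and PK samples, AEs after drug in All LY (b), and descriptive Week 52 scores for subjects who stop drug in Period 2. Most of it falls after Week 12. The subject numbers rest on assumed, independent miss rates with no other dropout. The 21.3 needs a 5% miss rate at every window and automatic removal.

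Imputed endpoints could change only for late attenders whom the off-window sentence below would keep on drug. They would no longer be scored as non-responders automatically.

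**What to change.** In Protocol 7.6:
- replace *discontinued from the study* with *discontinued from study treatment*;
- refer to 8.1.1 and Visits 801-804 for continued visits while the subject is willing and 8.2 does not apply;
- state that an off-window dose alone is recorded as a deviation and does not by itself require stopping drug or leaving the study.

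This is a wording change; the visits, the off-drug route and the IWRS status already exist. The costs are some extra visits, incomplete attendance, and the colonoscopy that the Schedule of Activities already asks for within 4 weeks of last dose in subjects who stop drug but stay on study. Little is gained for subjects whose noncompliance is with study procedures.
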